4.5 Recruitment

Phase I and II: Observational Cohort Study and Patient Journey Mapping

Research nurses will recruit and obtain consent from eligible women after they have been admitted to the facility for delivery and prior to discharge. Eligible women will be informed of the study and asked if they wish to participate. If the eligible participant is a minor, the parent or legal guardians(s) of the participant will be approached first by the research nurse. Consent will not be sought until after the patient has received an initial assessment by health workers at the time of admission for delivery, and research nurses may wait until after delivery to approach eligible women so as to not interfere with standard care. Women who suffer a loss or who are caring for a severely ill infant, will be given the option to defer the interview portion of data collection until the six-week postnatal follow-up period. During the consenting process, all women will be told they are free to withdraw from the study at any point without needing to give a reason for withdrawal. Data collected up to the point of withdrawal will be de-identified and retained for analysis.

Phase III: Process Mapping

Prior to the initiation of any study activities, healthcare providers and administrators will be notified of research activities through each respective hospital's human resources department. Process mapping participants will be asked to provide written informed consent at the beginning of the exercise. No identifying information of site staff participants will be collected or shared with participating facilities.

Phase IV: Focus Group Discussion

Caregivers/family members will be purposively selected to participate in FGD from a convenience sample of children enrolled in the initial phase of the study as a maternal infant dyad. The mother will be recruited by a research assistant who will brief her about the study at the time of discharge. If the mother verbally agrees, the research assistant will also ask for permission to contact the baby's father and grandmother for recruitment via phone.

4.6 Data collection

4.6.1 Training of research assistants

Research assistants will be trained by a study staff member in both quantitative and qualitative methodologies including process mapping facilitation, telephone interviewing, FGD facilitation, and direct patient observation. Ethical conduct regarding participant recruitment, consent, confidentiality, and data security will also be covered in training sessions. Research assistants will have clinical experience in the hospital environment and will be fluent in the dominant language spoken in the regions where each hospital is located.

4.6.2 Data Collection Tools

At the point of care, phase I and II data will be collected on a mobile device and phase III and IV data will be audio recorded. Data collection will be performed by dedicated study staff. Direct observations will be recorded in English using customized observation surveys and field logs. Patient interviews and observation surveys will collect patient demographic data and clinical data. Semi-structured phone interview guides will collect post-discharge process data. Data from process mapping exercises will be captured using paper-based worksheets and digital audio recordings. Audio from FGDs will be digitally recorded, transcribed verbatim in the language spoken during the recording and analyzed for emerging themes. Transcriptions will be translated to English (when needed) and de-identified prior to analysis.

4.6.3 Study Procedures

Phase I: Observational Cohort Study

I. Admission

- a. The study team will collect admission variables and health and pregnancy history through chart review and interviews with the participant. Data will not be collected during periods of maternal stress. In this case, incomplete interview questions will be deferred to the discharge interview.
 1. Admission variables: These questions include mode of transport, maternal demographic and socioeconomic variables (e.g., distance travelled to the hospital, age, location of residence). Data collected will also include vital signs (e.g., temperature, blood pressure, heart rate).
 2. Health and pregnancy history: This includes questions on number of previous pregnancies, comorbidities, prior admissions, and medication history.

II. Delivery

- a. Maternal variables: The study team will collect data related to the delivery including mode of delivery, method of induction, noted vaginal or perineal tearing, and any other major events or conditions occurring during delivery.
- b. Neonatal variables: Data will be collected related to the delivery including sex, Apgar score, weight, and resuscitation with oxygen therapy at birth.

III. Discharge

- a. Clinical Data Collection: A maternal and neonatal clinical examination will occur prior to discharge.
 1. Maternal Clinical Exam: Research nurses will record clinical signs and symptoms including SpO₂, heart rate, blood pressure, respiratory rate, and body temperature. We will also collect a small sample of blood (200 microlitres) to test hematocrit levels.
 2. Neonatal Clinical Exam: Research nurses will record clinical signs and symptoms data including weight, SpO₂, body temperature, and urination and defecation status. Data will also be collected on the infant's health status prior to discharge including NICU admission.
- b. Patient Interview: Following delivery, and prior to discharge, research nurses will conduct a structured interview and collect data including breastfeeding status, any symptoms experienced (e.g., headache, chest pain, difficulty emptying bladder, etc.).

IV. 6 Week Maternal and Newborn Follow-up (Outcomes)

- a. Telephone Interview: Research nurses and field officers will follow-up all dyads at 6 weeks postpartum to collect data on post-discharge care seeking and health outcomes, as well as newborn care practices. A verbal autopsy will be performed in all cases of newborn or maternal death. If

the mother or newborn was readmitted or died, data on clinical signs and symptoms and diagnoses during readmission or at death will be collected.

Phase II: Journey Mapping

- I. Journey mapping: We will ask a randomly selected group of mother-infant dyads (n=100) additional questions to ascertain their movement through the hospital, perspectives on the current system of post-natal care, and post-discharge pathways, at various time periods including in the postnatal patient interview, 72 hour post-discharge follow-up, and at the 6 week follow-up telephone interview.

Phase III: Process Mapping

- II. We will establish one working group (n=8) per facility who will be engaged in a process mapping exercise which is a qualitative methodology commonly used in quality improvement interventions. Process mapping exercises will be facilitated by a research assistant to gain an understanding of the post-natal discharge process as it currently operates and to identify inefficiencies to care and potential solutions. Working groups will engage in a brainstorming session using paper, pens, and sticky notes to map out the discharge pathways of their respective facilities. Group members will work together to identify all stages of the process and indicate the individuals involved at each stage. When the working group reaches consensus and deems the flowchart complete and accurate, it will then be analyzed by members to identify problems, bottlenecks, and non-value-added steps such as unnecessary work, duplication, or communication breakdowns. After process inefficiencies are identified, teams will brainstorm, first individually then as a group, to identify potential solutions. The process mapping exercise will take 90-120 minutes per facility. The facilitator will use prompts to motivate participants to discuss topics in greater detail as needed. All process data will be mapped to a stage of the discharge process to provide a comprehensive model of post-natal discharge processes from the provider perspective.

Phase IV: Focus Group Discussion

We will conduct focus group discussions with mothers and family members to explore needs and the value of post-discharge care, and social and economic barriers to seeking this care. For teenage mothers, as teenage pregnancy is associated with trauma, stigma, and discrimination, these participants may experience distress during the FGD. To mitigate this, FGDs for teenage mothers will be separated from adult mothers. Research Assistants (RAs) will be trained by an experienced qualitative researcher on how to ensure that the rights of subjects and confidentiality of data are protected and respected. RAs will be

instructed on how to create an open, inclusive, and confidential space with participants at the beginning of the discussion as well as how to intervene if the discussion becomes discriminatory towards other participants. RAs will reassure participants that their participation is entirely voluntary and that they can withdraw from the study at any time. If participants experience negative feelings during the discussion, they will be referred to the facility's medical social worker for counselling.

Focus groups will begin with questions and conversations to build trust among participants. For mothers, grandmothers, and fathers, discussions will focus on illness recognition, health seeking/decision-making, postnatal care interventions, and interactions with the health system during the peri and post-discharge period. Data collected will include questions about the hospital stay, communication with the healthcare team, the discharge process, barriers faced upon discharge, and post-discharge PNC visits. Discussions will be conducted in the primary local language (e.g., Runyankole and Lusoga), audio-recorded, transcribed, and translated to English.

4.7 Study Outputs

Phase I: A pair of internally validated prediction models (one each for mom and baby) for identifying dyads at high-risk of death or hospital readmission after discharge following live birth in-hospital. Our candidate predictors for our models will be maternal and infant characteristics collected at the time of admission and discharge following a facility delivery.

Phase II-IV: A descriptive account of all aspects of the discharge process and postnatal care follow-up visits for facility-based deliveries, including identification of barriers and solutions to effective postnatal care from the perspective of patients, caregivers, and facility staff. We will use this information to inform the development of a bundle of interventions, with separate components for high-risk mothers and high-risk newborns, and a locally supported and culturally safe strategy for implementing this bundle of interventions.

4.8 Outcomes (Phase I)

The primary outcome is maternal and/or neonatal death or need for re-admission within six weeks of birth.

Secondary outcomes include:

1. Post-natal care visits during the 6-week post-discharge period
2. post-discharge health seeking practices for mothers/newborns during the 6-week post-discharge period
3. Causes of readmission/mortality among those who experience such outcomes, based on verbal autopsies and admission symptom/diagnosis questionnaires

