The first 6 weeks after birth remains a critical period of vulnerability for mother-newborn dyads. The WHO recommends at least 4 postnatal check-ups at a facility or by a community health worker in the first 6 weeks after birth. Yet this is not possible for many dyads because of overburdened health systems and scarce family resources. Personalized risk scores can help frontline healthcare providers identify high-risk mother-newborn dyads before discharge from hospital, and guide recommendations for essential postnatal care. The health of a child is closely linked to the health of its mother, so it is essential that we consider the mother and child as a dyad. Here, we aim to develop a risk predictive algorithm that integrates data about the health of the mother and newborn to identify mother-newborn dyads who are at a high-risk of dying or hospital readmission during the post-delivery, post-discharge period. This is a mixed-method study at two hospitals in Uganda. We will conduct an observational cohort study to develop and internally validate our risk score and aim to recruit 7000 mother and newborn dyads from Jinja Regional Referral Hospital and Mbarara Regional Referral Hospital. We will engage with patients, families, and health workers through direct observation, journey mapping, process mapping, and focus group discussions to identify gaps and opportunities during in-hospital, discharge, and post-discharge care for informing the development of an evidence- and risk-based bundle of interventions to improve postnatal care (PNC) for dyads. We will leverage our experience developing, validating and implementing an innovative precision public health approach for improving post-discharge care for children in Uganda following hospitalization for severe infection. Ultimately, our personalized risk score, combined with interventions that target prevention or treatment of critical causes of death or illness, will inform evidence-based recommendations for PNC, and improve health outcomes for dyads. Treating the mother and newborn as a dyad ensures that when one is sick, the other can be more closely monitored to prevent their potential decline in health.

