Currently, the World Health Organization (WHO) recommends three in-person postnatal visits for all mothers and newborn infants born at a health facility within the first six weeks of life⁶. The evidence used in formulating this recommendation is primarily based on timing of maternal and neonatal deaths and evidence surrounding the efficacy of the components of care recommended during the postnatal period. Despite this WHO recommendation, achieving any postpartum follow-up care has been challenging in many low-resourced settings. For example, in Uganda, only 57% of women received one visit with a skilled health care provider within 41 days of delivery³. There is an important opportunity to tailor recommendations for timing and frequency of follow-up to individual risk, to guide the use of scarce healthcare resources. Personalized risk scores can help frontline healthcare providers identify high-risk dyads before discharge from hospital, and guide recommendations for essential PNC. This approach facilitates safer hospital to home transitions and efficient allocation of scarce resources. Adherence to the recommended PNC visits is critical for those at higher risk.

The development of an evidence base upon which to build recommendations for the timing and intensity of postnatal care in resource-poor countries is urgently needed. This study aims to address this gap in care coverage using a precision medicine approach to postpartum follow-up. Our approach to risk stratification integrates data about the health of both the mother and newborn. This ensures that when one is sick, the other can be more closely monitored to prevent their potential decline in health. We are working to expand our innovative precision public health approach to improving post-discharge care for mother-newborn dyads. Our aim is to build a discharge risk prediction score that identifies high-risk dyads before hospital discharge. To achieve this, we will conduct an observational cohort study in 7,000 dyads discharged together after live births at JRRH and MRRH. With the data collected from this study, we will be able to develop prediction models with up to 30 candidate predictors for both maternal and newborn outcomes separately.

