2.0 CHAPTER TWO: Problem statement, justification, and conceptual framework

2.1 Problem statement

Neonatal outcomes are highly correlated with the health of the mother, an example of this is shown repeatedly by poor rates of survival of infants after maternal death^{1,2}. Prediction of risk, based on the mother and infant as a pair, is a major gap in current research and yet vital to the survival of both the mom and the infant. In our prior epidemiological study of post-discharge outcomes among 3,236 dyads, we found that most readmissions were due to infectious illness and occurred early in the post-discharge period. Of the 2,926 dyads with complete follow-up data 7.1% of dyads reported at least 1 outcome. 3.6% of newborns were readmitted, 0.8% died, and 2.7% of mothers were readmitted. For readmitted newborns, the most common diagnosis was sepsis (63%), and 19% were in respiratory distress at readmission. For readmitted mothers, the most common diagnoses were surgical site infections (51%), puerperal sepsis (43%), malaria (19%), and other infections (5%). Considering the health of the mother and newborn as a dyad is an innovative and effective approach as the health of a child is closely linked to the health of its mother. A mother's morbidity or mortality affects the health of all her children – and newborns whose mothers died during the first 6 weeks have an even greater risk of dying than those whose mothers survive¹⁵. Thus, we can improve maternal and child health outcomes by identifying both mothers and babies at increased risk of mortality or serious morbidity after hospital discharge and allocating scarce resources for targeted follow-up to those most vulnerable. This allows us to not only improve health outcomes but benefits the health system with efficient use of resources.

[figure not shown]

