3.0 CHAPTER THREE: Research Question and Objectives

3.1 Hypothesis

Maternal and infant characteristics collected at the time of discharge following a facility delivery can predict the risk of maternal or neonatal death or need for re-admission within six weeks of birth.

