3.2 Objectives

Our primary objective is to inform the development of an integrated maternal and newborn risk-based post-discharge care program. Specifically, we aim to (1) develop and internally validate clinical risk prediction models for identifying dyads at high-risk of death or hospital readmission in the 6 week post-delivery post-discharge period, and (2) identify gaps and opportunities during in-hospital, discharge, and post-discharge care to inform the future development of an evidence-and risk-based bundle of interventions to improve PNC for dyads.

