4.9 Study Limitations

This study is subject to several potential limitations. First, losses to follow-up may reduce our effective sample size, thus diminishing our power to detect significance in some variables. However, our prior work in this area suggests that our losses to follow-up will be less than 5%. Furthermore, our study sample size has compensated for these potential losses to follow-up and we thus do not anticipate this to be an issue. Second, heterogeneity in outcomes may impact modelling of post-discharge events. We observed this to be a potential limitation in our prior work, in that the predictors were different between newborns and mothers, and even among mothers, between those with caesarean sections and those who delivered vaginally. To improve our probability of success, therefore, our sample size was developed to be able to model at least 3 separate outcomes. We anticipate that this will be sufficient to create a set of models which are comprehensive to capture various outcomes. Finally, With limited numbers of focus group discussions, this study may not reach thematic saturation. If this is deemed to be the case we will add additional focus groups, following a protocol amendment.

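### The primary outcome counts any death within six weeks of birth, while the aims and the discharge score concern events after discharge

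*Combined protocol and SAP*

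**What the plan says.** Two places start the clock at birth and place no discharge condition on death. Section 4.8 reads "The primary outcome is maternal and/or neonatal death or need for re-admission within six weeks of birth". The hypothesis in 3.1 says that characteristics taken at discharge "can predict the risk of maternal or neonatal death or need for re-admission within six weeks of birth".

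Other places concern events after discharge:
- The Abstract aims to find dyads "at a high-risk of dying or hospital readmission during the post-delivery, post-discharge period".
- Aim 1 in 3.2 is about "identifying dyads at high-risk of death or hospital readmission in the 6 week post-delivery post-discharge period".
- The Phase I output in 4.7 is a pair of models for "death or hospital readmission after discharge following live birth in-hospital".
- Section 4.9 warns that "heterogeneity in outcomes may impact modelling of post-discharge events".
- Chapter 1 describes the cohort thus: "we will conduct an observational cohort study in 7,000 dyads discharged together after live births at JRRH and MRRH".
- The planning rates in 2.1 come from a prior study of post-discharge outcomes: "3.6% of newborns were readmitted, 0.8% died, and 2.7% of mothers were readmitted".

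The follow-up call also has two anchors. Section 4.1 and Appendix A set it six weeks after discharge, and 4.6.3 sets it six weeks after birth.

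**The concern.** A score calculated at discharge can only be used for people who reach discharge. If deaths before discharge count as events, three things follow.

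- **Validity of the prediction.** Someone who dies first may have no discharge examination. Some discharge items, such as maternal discharge status and the baby's disposition, have death among their categories. Used as predictors, those categories would be the outcome itself.
- **Reported performance.** Sensitivity, specificity and AUROC would partly describe cases for which the score has no use.
- **Comparability.** The event rate would no longer be of the same kind as the rates in 2.1.

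Sections 4.8 and 4.10 are where an analyst would look for the definitions to code. There, a literal reading of the stated rule departs from the aims.

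**Working it through.** **The plan's own precision figure.** Section 4.4 claims a margin of error within 1%. The 95% margin is 1.96 × √(p(1−p)/n).
- Dyads, p = 7.1% (2.1), n = 7,000: 1.96 × √(0.071 × 0.929 / 7,000) = 0.60%.
- The same with 5% lost (the upper limit in 4.9), n = 6,650: 0.62%.
- Newborns at 4.4% and mothers at 2.7%, n = 6,650: 0.49% and 0.39%.

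The claim is reproduced and holds under the post-discharge definition. The point is therefore about definition and not about precision.

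**Does any rule remove deaths before discharge?**
1. *Enrolment (4.5).* Women are recruited between admission and discharge, and those who suffer a loss stay in with a deferred interview. A death in hospital after enrolment is therefore possible.
2. *Eligibility (4.4).* The inclusion criterion asks only for delivery at the study hospital. A later sentence mentions babies who die after discharge, but it is a follow-up rule.
3. *Outcome (4.8).* The primary outcome has no discharge condition for death. Secondary outcomes 1 and 2 have post-discharge windows, but these do not govern the primary outcome.
4. *Analysis (4.10).* No risk set or time zero is given.
5. *Data (Appendix A).* The re-admission items ask about admissions after being home, so only deaths are affected. Whether the baby was born alive, maternal discharge status, the baby's disposition and whether the newborn was ever discharged are all recorded. No text says how they are used.

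The data to apply the intended definition are largely there; the rule is not.

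**Scale.** The rates in 2.1 give planned newborn events of (3.6% + 0.8%) × 7,000 = 308, or 293 with n = 6,650. Adding the two rates assumes that no readmitted newborn died. If every death were in a readmitted newborn, the total would be 3.6% × 7,000 = 252.

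The documents give no pre-discharge death rate r, so the values below are assumptions. Extra deaths are r × 7,000. Their share of newborn events is s = r / (r + 4.4%).

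| Assumed r | Extra deaths | Share s |
|---|---|---|
| 0 (post-discharge reading) | 0 | 0% |
| 0.1% | 7 | 7/315 = 2.2% |
| 0.25% | 17.5 | 5.4% |
| 0.5% | 35 | 10.2% |
| 1% | 70 | 18.5% |

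With full overlap, the 0.1% row becomes 7/259 = 2.7%.

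**Performance, as an illustration.** Section 4.10 seeks sensitivity above 80%. Suppose the model flagged every pre-discharge death, which is an extreme assumption. Apparent sensitivity is then s + (1−s) × true sensitivity, and an apparent 80% corresponds to a true (0.80−s)/(1−s). This is 79.5% at s = 2.2%, 77.7% at s = 10.2% and 75.5% at s = 18.5%. If such cases dropped out for lack of discharge data, there would be no such bias.

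**Call anchor.** A call at day 42 after birth covers 42 minus length of stay in post-discharge days. For assumed stays of 1, 3, 7 and 14 days that is 41, 39, 35 and 28 days. The six-week window from birth is complete in each case; the six-week post-discharge window of secondary outcomes 1 and 2 is not.

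**The case against.** The strongest reply is that the intended reading is plain. Section 4.7, directly before 4.8, defines the models by events after discharge following live birth. Chapter 1 limits the cohort to dyads who leave together after live births. The hypothesis takes its predictors at discharge. Aim 1's window can be read as running from discharge to six weeks after birth. No pre-discharge death rate is available, so no harm is demonstrated.

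Most of this stands, and it limits the point to a conflict of wording with an unknown effect. It does not remove the point, because the outcome as written includes deaths that the aims exclude, and no analysis rule resolves the difference.

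A reader might infer more than the documents support:
- *That discharge is ignored throughout 4.4 and 4.8.* It is mentioned in both, though not as a primary-outcome or risk-set rule.
- *That many stillbirths will enter the cohort.* The stillbirth figure in 2.2 is national, and that section treats stillbirth as a later extension.
- *That most maternal events will precede discharge.* Chapter 1 says 30% of mothers who die in the first six weeks do so after 24 hours, and that facilities in the region routinely discharge within 24 hours. Neither statement gives a pre-discharge death rate for these two hospitals.
- *That a maternal date of death is missing.* Appendix A does not list one separately, but every maternal death has a verbal autopsy whose contents are not shown.

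The call anchor is rightly called minor, and it can be reconciled in more than one way.

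**Conclusion.** The conflict is real and should be fixed before analysis. Sections 3.1 and 4.8 count any death in six weeks from birth; the Abstract, 3.2, 4.7 and 4.9 concern events after discharge; and 4.10 does not choose between them. The effect runs from zero, if the analysts follow the aims, to an unknown amount if they code 4.8 literally. The scale of about 2% of newborn events per 0.1% of pre-discharge newborn mortality rests on the prior-study rates and on no overlap between readmission and death. It is not an estimate of what will happen.

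The documents do not support saying that the investigators mean to predict in-hospital deaths, or that the stated precision fails. The two call anchors leave the primary window intact and shorten secondary outcomes 1 and 2 by the length of stay if the call is made at six weeks after birth.

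**What to change.** 1. In 3.1 and 4.8, define the event as *death or re-admission after discharge following birth and up to six weeks after birth*.
2. In 4.10, restrict each model to members discharged alive following a live birth, with time zero at discharge. Use the born-alive, discharge-status, disposition and never-discharged items already in Appendix A. Do not use the death categories of these items as predictors. Say how the referral and against-advice categories of discharge status are classed. Report stillbirths and pre-discharge deaths descriptively.
3. Reconcile this risk set with the Chapter 1 description of dyads discharged together. State whether mothers and babies who leave separately are in their respective models. The forms foresee a baby in NICU (Appendix A) and an infant discharged after the mother's death in hospital (Appendix B). If babies who leave separately are included, record their own discharge date, because Appendix A captures it under the mother.
4. Bring the call (4.1, 4.6.3, Appendix A) and the windows of secondary outcomes 1 and 2 to one anchor. If the call may fall later than six weeks after birth, make sure that event dates, including maternal date of death, are available to cut the primary outcome at six weeks.

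The cost is a few sentences, one filter per model and possibly a date field. The downside is slightly fewer analysable members.
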